3.2 Rationale for the Trial

...

The guardian™ 4 trial is a prospective clinical phase 3a trial intended at demonstrating safety and efficacy of turoctocog alfa in PUP < 6 years of age with severe haemophilia A.

4.2 Endpoint

.....

Primary Endpoint

1. Incidence rate of FVIII inhibitors ($\geq 0.6 \text{ BU/mL}$) will be evaluated for the main phase of the trial.

.....

Safety Endpoints:

.....

- Incidence rate of clinically relevant inhibitors defined as an inhibitor titre ($\geq 0.6 \text{ BU/mL}$) combined with a decreased recovery (<66% of expected level)

- Incidence rate of high-titre inhibitors defined as inhibitor titre $\geq 5 \text{ BU/mL}$.
- Incidence rate of FVIII inhibitors ($\geq 0.6 \text{ BU/mL}$)

5.3.1 Preventive Treatment and Dose Adjustment

The preventive treatment regimens are meant to reflect the different dosing regimens applied globally for initial and continued treatment of PUP. The recommended dose is 15-50 IU/kg BW once weekly at the start of preventive treatment, but ~~higher and~~ more frequent doses may be necessary depending on the clinical situation. The regimen should then be gradually increased towards 20-50 IU/kg BW every second day or 20-60 IU/kg BW *two or three times weekly*.¹⁴

The decision to initiate preventive treatment will be made by the Investigator and the child's parent or legal representative with due consideration for the child's own wishes (if they are capable to express these wishes). However, the preventive treatment has to be commenced no later than when the patient reaches 24 months old, or after a maximum of two ~~treatment requiring bleeding episodes have occurred which require treatment with turoctocog alfa (joint, muscle or severe bleeding episode) have occurred~~, whatever comes first. Should a patient be older than 24 months of age at enrolment, preventive treatment needs to start immediately

5.3.2 Treatment of Bleeds and dose adjustment

.....

The dose for treatment of bleeds should aim at providing a post injection level of FVIII of at least 0.50 IU/mL or 50 IU/dL. ~~The bleeding pattern of the individual patient, as well as low trough levels described above, should be considered in adjustments of the preventive dose and at the Investigator's discretion.~~

The individual dose is determined by the investigator, using the recommendations in the World Federation of Haemophilia (WFH) guidelines.¹⁰

The required dosage can be determined using the following formula

Dose (IU) = weight (kg) x desired factor level (IU/dL) x 0.5

The WFH guideline¹⁰ may be used to guide dosing. FVIII activity should not fall below the lower range for the given plasma activity level (in % of normal or IU/dL) until the bleeding episode is resolved. As the guidelines are recommendations non-compliance with them will not require protocol deviations. The maximum dose per injection mentioned in this protocol must though be followed.

Table 5-1 *Guide for dosing in bleeding episodes¹*

Degree of haemorrhage	FVIII level required (%) (IU/dl)	Frequency of doses (hours)/ Duration of therapy (days)
Early haemarthrosis, muscle bleeding or oral bleeding	20-40	Repeat every 12 to 24 hours until the bleeding episode as indicated by pain is resolved or healing achieved
More extensive haemarthrosis, muscle bleeding or haematoma	30-60	Repeat injection every 12 to 24 hours for 3-4 days or more until pain and acute disability are resolved
Life-threatening haemorrhages	60-100	Repeat injection every 8 to 24 hours until threat is resolved

X¹ Novo Nordisk company core data sheet for turoctocog alfa

This formula may be used to calculate resulting factor levels:

IU/dL (or % of normal) = [Total Dose (IU)/body weight (kg)] x 2 [IU/dL]/[IU/kg]

.....

Each administered dose (mL IU-given, vial strength and time of day) as well as efficacy in treatment of bleeds will be registered in the diary and in the eCRF.

5.3.3 Treatment during surgery

.....

Doses should aim at securing haemostasis without reaching super-physiological FVIII levels.

5.3.4 Treatment of patients with inhibitors

.....

An ITI protocol with high-dose or low-dose regimen can be chosen by the Investigator, depending on the patient's peak inhibitor titre and the titre before the start of the ITI. International consensus guidelines and local practice guidelines should be used when selecting optimal ITI regimen.^{15, 16, 17}

.....

Patients will be evaluated after 12 months of ~~ITI~~ inhibitor treatment, based on the level of inhibitors. If inhibitors are still positive after 12 months, but the decline from peak titer level is \geq 20%, ~~ITI~~-inhibitor treatment may continue for a maximum period of 24 months in total.

The dose level and dosing frequency of inhibitor treatment will be decided by the Investigator based on clinical evaluation and local standards, and it should be documented in the eCRF. Within this trial, 'inhibitor treatment' includes Immune Tolerance Induction (ITI) as well as smaller dose adjustments with ~~low responding and/or clinical insignificant~~ inhibitors.

If needed and decided by the Investigator, the initiation of the inhibitor treatment with turoctocog alfa can be delayed, but it has to start within 6 months from the time of diagnosis of inhibitor.

Inhibitor treatment with turoctocog alfa will be included in the overall count of ED.

If the inhibitor disappears ($\text{BU} < 0.6 \text{ BU/mL}$) during the *inhibitor ITI*-treatment, the patient will continue in the extension phase at a time point decided by the Investigator, resuming/starting preventive treatment as recommended in this protocol, see Table 2–1. However, if the inhibitor persists after 24 months of ~~ITI~~-inhibitor treatment, the patient will be withdrawn from the trial.

Table 2–1 Overview of Treatment Regimens

Trial product	Dose	Treatment	Type	Total daily Doses, IU/kg	Frequency	Targeted level of FVIII
rFVIII (turoctocog alfa)		Preventive	Individual	15-50	Once weekly	Local practice & guidelines
rFVIII (turoctocog alfa)		Preventive	Individual	20-60	Two times weekly	Local practice & guidelines

rFVIII (turoctocog alfa)	Preventive	Individual	20-60	3 times weekly	Local practice & guidelines
rFVIII (turoctocog alfa)	Preventive	Individual	20-50	Once every second day	Local practice & guidelines
rFVIII (turoctocog alfa)	Treatment of bleeds	Individual	Investigator's discretion **. See section max 2x100	Investigator's discretion	>0.50 IU/mL
rFVIII (turoctocog alfa)	Surgery	Individual	Investigator's discretion** max 2x100	Investigator's discretion	>0.50 IU/mL* Local practice & guidelines
rFVIII (turoctocog alfa)	Inhibitor	Individual	Investigator's discretion**	Investigator's discretion	NA

* Pre-surgery and during surgery treatment

** Please see section 5.3 for the maximum allowed dose

6 Trial population

6.1 Number of Patients to be studied

.....

Planned number of trial sites: 505

6.2 Inclusion Criteria

.....

4. No prior use of purified clotting factor FVIII products (previous exposure, equal to or less than 5 ED to blood components, e.g. cryoprecipitate, fresh frozen plasma, is accepted) *including commercially available NovoEight®/Novoeight®*

2.4 Withdrawal criteria

.....

5. Inhibitor treatment has not been started within 6 months from the date of confirmation of positive FVIII inhibitor (~~BU~~ ≥ 0.6 BU/mL)

6. FVIII inhibitor titer decline from peak level is less than 20% after 12 months of inhibitor treatment
7. FVIII inhibitor is positive ($BU \geq 0.6 \text{ BU/mL}$) after 24 months of inhibitor treatment.
8. After completed inhibitor treatment (maximum 24 months), preventive treatment as described in the protocol is not resumed/started.
9. *Preventive treatment not initiated at the patient's age of 24 months.*

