The maximum total daily dose of ~~N8 turoctocog alfa~~, for the treatment of bleeds *and/or during immune tolerance induction treatment for patients with inhibitors*, is 200 IU/kg with a maximum dose per infusion of 100 IU/kg. ~~This maximum limit does not apply during inhibitor treatment for patients with inhibitors~~

2.13 5.3.4 Treatment of Patients with Inhibitors

Several genetic factors, such as FVIII gene mutation type, family history of inhibitors, ethnicity, have been associated with inhibitor development in patients with severe haemophilia.¹⁵

Management of patients with inhibitors includes the treatment of bleeding episodes by the use of by-passing agents (rFVIIa or activated prothrombin complex concentrates) and the permanent eradication of the inhibitor through immune tolerance induction therapy.

Patients who develop inhibitors, within this trial, will be offered continued treatment with ~~N8 turoctocog alfa for 12 months. The duration of the inhibitor treatment will be at least 12 months from the time of diagnosis of inhibitor. For patients who develop inhibitors during their first year in the trial (within 12 months) the inhibitor treatment may continue until a total trial duration of 24 months.~~

It may also be decided by the Investigator and/or parent/legal representative to withdraw the patient.

Transient inhibitors are defined in this trial as inhibitors which disappear within 3 months after two positive inhibitor tests.

~~Inhibitor treatment success is defined as (not applicable for patients with transient inhibitors):~~

[figure not shown]
- ~~two consecutive blood samples showing inhibitor level <0.6 BU/mL~~
- ~~FVIII plasma recovery ≥66 % of expected level~~
- ~~N8 T1/2 of ≥6 h after a 72 h N8 washout period¹⁷~~

~~Inhibitor treatment failure is defined as persistence of inhibitor with no consistent decline of the inhibitor titer from peak level within 12 months of the inhibitor diagnosis. If inhibitor treatment failure occurs, the patient must be withdrawn.~~

After completion of the inhibitor treatment, *or if preventive treatment is resumed*, the patient will be called to an End of trial Visit (Visit 5 7).

Treatment of bleeds with by-passing agents i.e. rFVIIa or activated prothrombin complex concentrate (APCC), is allowed for patients who develop inhibitors.

Details on inhibitor management can be found in Figure 5.1

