2.39 19.1 Informed Consent Form for Trial Patients	20

2.40	19.4 Regulatory Authorities.....	21
2.41	20 Premature Termination of the Trial/Trial Site	21
2.42	23 Responsibilities	21
2.43	25 Retention of Clinical Trial Documentation.....	22
2.44	Attachment I – Global.....	22

Table of figures

	Page
Figure 12–1	17

Table of tables

	Page
Table 2–1 Visit Flow Chart main trial phase	6
Table 2–2 Visit Flow Chart trial extension phase	6

1 Introduction including rationale for the protocol amendment

The main reasons for this amendment is to re-define the duration and conditions for treatment of patients with inhibitors, restrict the number of previous exposures to blood components (to keep a homogenous PUP population), re-define the trial duration and revise the date of end of trial. In addition, the possibility to further investigate immunogenicity of turoctocog alfa e.g. non-neutralising antibodies assessment and Human Leucocyte Antigen (HLA) genotyping will be introduced. Some changes are administrative to align with updated guidelines and Novo Nordisk Standard Operation Procedures e.g. the requirement to list the participating countries has been removed.

The Patient Information and Informed Consent will be adapted accordingly.

In this protocol amendment:

- Any new text is written ***in italics***.
- Any text deleted from the protocol is written using **strike through**.
- Corrections of minor inconsistencies and ambiguities, and typographical errors will not be listed.

2 Changes

2.1 1 Summary

Trial Design

The trial consists of two phases. In the main phase, an aggregated number of at least 50 patients will receive preventive treatment with turoctocog alfa until they reach a minimum of 50 exposure days² (ED) or until they develop inhibitors. After that the patients will continue in the extension phase ~~until where at least 50 patients should achieve~~ at least 100 ED ~~has been achieved~~, which will translate into a ~~maximum~~ trial duration of up to 3.5 5 years (*including any potential inhibitor treatment*). The estimated total duration of the trial is approximately 5 7 years.

Trial Population

Approximately 60 PUP with severe (FVIII \leq 1%) haemophilia A with no history of inhibitors below 6 years of age ~~in a non-bleeding state~~ will be enrolled to allow for at least 50 patients to complete the trial

Key Inclusion Criteria

- ---

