Screening will be done at Visit 1. Visit 2 will be performed within 21 days post Visit 1, and it could be the same day as Visit 1. At Visit 2 eligible patients are enrolled and preventive treatment with investigational product (turoctocog alfa) starts if applicable (may be delayed, see section 5.3.1 start after the first two bleeds). At Visit 5, after \geq 50 ED, patients will leave the main phase of the trial and continue in the extension phase. Patients who develop inhibitors can continue with ITI treatment with an alternative visit schedule (down ward arrows). If ITI treatment is successful these patients can continue with preventive treatment according to the extension phase (upward arrows). The patients will belong to either of the groups main phase, extension phase or inhibitor cohort.

2.3 5.1 Type of Trial

The main trial phase will be completed when the aggregated number of patients, who have either received treatment with turoctocog alfa for at least 50 ED or developed inhibitors, are at least 50. In the extension phase, *at least 50* the patients will be followed until at least 100 ED has been achieved. For the individual patient it translates into duration of the main phase of approximately 3-24 months depending on the dose regimens (and bleeding pattern). The duration of the extension phase may be up to 3.5 years, and the total duration of the trial is estimated to be approximately 5-7 years, please see Section 7.

2.4 5.3 Treatment of Patients

Patients will enter a bleeding preventive regimen as described below, see Section 5.3.1. ~~Preventive treatment can be postponed until a maximum of two bleeding episodes have occurred.~~ For prevention one single bolus dose of turoctocog alfa is administered intravenously (i.v.) at each administration day. Turoctocog alfa should preferably be administered in the morning. The maximum duration of treatment of a patient from first to last turoctocog alfa administration is approximately 4 years.

2.5 5.3.1 Preventive Treatment and Dose Adjustment

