Treatment of bleeds with by-passing agents i.e. FVIIa or activated prothrombin complex concentrate (APCC) *according to local label*, is allowed for patients who develop inhibitors. *Bypassing agents are not considered trial medication*

2.8 5.4 Treatment after End of Trial

When discontinuing trial product, patients should be switched to a suitable marketed product at the discretion of the Investigator. It is expected that turoctocog alfa will be granted marketing authorisation and is commercially available when the patients complete this trial. *However, this cannot be guaranteed.*

Novo Nordisk will not provide any patient with trial medication after the end of the trial unless required in accordance with local law or regulation.

2.9 6.1 Number of patients to be Studied

Countries planned to participate: Austria, Brazil, China, Croatia, Greece, Hong Kong, Japan, Russia, Spain, Turkey, and US.

Planned number of patients to complete the main phase of the trial: 50

2.10 6.2 Inclusion Criteria

4. No prior use of purified clotting factor products (previous exposure, *equal to or less than 5 ED* to blood components, *e.g. cryoprecipitate, fresh frozen plasma*, is accepted)

2.11 6.4 Withdrawal criteria

A patient must be withdrawn if the following applies:

1. Not in use
2. Allergy/Anaphylaxis to the trial product
3. Treatment with FVIII products other than turoctocog alfa
4. Not in use
5. *Inhibitor treatment has not been started within 6 months from the date of confirmation of positive FVIII inhibitor (BU \geq 0.6/mL)*
6. *FVIII inhibitor titer decline from peak level is less than 20% after 12 months of inhibitor treatment*
7. *FVIII inhibitor is positive (BU \geq 0.6/mL) after 24 months of inhibitor treatment.*
8. *After completed inhibitor treatment (maximum 24 months), preventive treatment as described in the protocol is not resumed/started.*

2.12 6.6 Rationale for Trial Population

Rational for Withdrawal Criteria

- *Criterion no. 5-8 are selected for the safety of patients, who do not benefit from inhibitor treatment with turoctocog alfa*

2.13 7 Trial Schedule

Planned date for LPLV: **QIII 30 June 2016** *2018*

~~The duration of the trial for the individual country is dependent upon the timelines of market authorisation and commercial availability of the trial product. Should market authorisation not be obtained, the maximum trial duration is approximately 5 years.~~

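### Minor wording gap: withdrawal criterion 5 and the six-month start rule ignore the current titre, so a boy whose confirmed inhibitor cleared without recorded inhibitor treatment must be withdrawn

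*Combined protocol and SAP*

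**What the plan says.** Section 6.4, as worded in the amendment that follows Amendment 7, lists conditions under which a patient must be withdrawn. Criterion 5 is that "Inhibitor treatment has not been started within 6 months from the date of confirmation of positive FVIII inhibitor"; the 0.6 BU/mL threshold attached to it describes the confirming result. Section 5.3.4 in the same amendment says that the start of inhibitor treatment "can be delayed, but it has to start within 6 months from the time of diagnosis of inhibitor".

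Other places bear on how far these rules reach:

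- **Transient inhibitors.** "Transient inhibitors are defined in this trial as inhibitors which disappear within 3 months after two positive inhibitor tests" (5.3.4, shown in Amendment 1).
- **What counts as treatment.** Inhibitor treatment "includes Immune Tolerance Induction (ITI) as well as smaller dose adjustments with" inhibitors (5.3.4); the restriction to low-responding or clinically insignificant inhibitors was struck.
- **Return to the extension phase.** If the inhibitor falls below 0.6 BU/mL during inhibitor treatment, "the patient will continue in the extension phase at a time point decided by the Investigator" (5.3.4). Section 8.1.6 and the lead-in to Table 2-2 also tie this return to inhibitor treatment.
- **General route.** After 50 ED or an inhibitor, "After that the patients will continue in the extension phase" (Summary, Trial Design, Amendment 7), where inhibitor treatment is mentioned only as a possibility.
- **Rationale.** Criteria 5 to 8 "are selected for the safety of patients, who do not benefit from inhibitor treatment with turoctocog alfa" (6.6, Amendment 7).
- **Testing.** In the latest amendment, 8.1.5.2 lists the inhibitor test among the assessments for inhibitor unscheduled visits, which must occur at least three-monthly. Table 2-3 marks the same test as optional.

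**The concern.** A transient inhibitor rests on two positive tests, which is also how 8.2.2.1 defines a diagnosis. A transient case is therefore a confirmed case, and confirmation starts the six-month clock. If the investigator watches and waits and the titre clears, criterion 5 still applies at month 6, although there is nothing left to treat. Withdrawal would then depend on whether the site had recorded a dose change as inhibitor treatment.

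The loss would be long-term information on a boy of particular interest. The extension phase tests for inhibitors at least twice a year, and those tests would show whether a cleared inhibitor returns. He might also be lost from the group of at least 50 for whom Amendment 7 says "the patients will be followed until at least 100 ED has been achieved" (5.1).

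**Working it through.** The plan states no figure on this point. The check is a comparison of texts, followed by arithmetic on exposure days.

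**1. Titre conditions in section 6.4**

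| Criterion | Time point | Depends on titre at that time? |
|---|---|---|
| 5 | 6 months after confirmation, no treatment started | No |
| 6 | 12 months of inhibitor treatment | Yes: decline from peak under 20% |
| 7 | 24 months of inhibitor treatment | Yes: still at or above 0.6 BU/mL |

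Criterion 5 is the only one of the three that does not look at the current titre.

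**2. Timeline.** A transient inhibitor is gone by month 3 and criterion 5 applies at month 6. The boy has then been inhibitor-free for at least 6 - 3 = 3 months.

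**3. Search for an exemption.** The only wording that set transient inhibitors apart belonged to the definition of treatment success, which Amendment 1 deleted. The latest amendment changes neither criterion 5 nor the start rule. The Summary's general route does not override a mandatory withdrawal rule.

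**4. Exposure days at month 6.** Inputs: Visits 3 and 4 fall at 10-15 and 20-25 ED, so confirmation is taken at 10-25 ED; Visit 5 falls at 50-55 ED (Table 2-1). Regimens come from 5.3.1. Assumptions: 26 weeks (182 days), regimen unchanged, no bleed or surgery days, which would add ED.

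ED at month 6 = ED at confirmation + ED added.

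| Regimen | ED added | From 10-25 ED | Short of 100 | From 50-55 ED | Short of 100 |
|---|---|---|---|---|---|
| Once weekly | 26 x 1 = 26 | 36-51 | 49-64 | 76-81 | 19-24 |
| Twice weekly | 26 x 2 = 52 | 62-77 | 23-38 | 102-107 | 0 |
| Three times weekly | 26 x 3 = 78 | 88-103 | 0-12 | 128-133 | 0 |
| Every second day | 182 / 2 = 91 | 101-116 | 0 | 141-146 | 0 |

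The regimen is held unchanged on purpose: an increase after confirmation could itself be recorded as inhibitor treatment, and the rule would then not apply.

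**5. How many boys.** At the stated 30-35% inhibitor rate, 60 enrolled gives 60 x 0.30 = 18 to 60 x 0.35 = 21 confirmed cases. The share that clears with no recorded treatment is not in the documents. If it were 0%, 10%, 20% or 30%, the expected number would be 0, 1.8-2.1, 3.6-4.2 or 5.4-6.3. These shares are illustrations, not estimates.

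**The case against.** The strongest reply is that the rule will rarely be reached. Inhibitor treatment includes small dose adjustments, 5.3.1 asks investigators to raise the preventive regimen gradually, and regimen changes are documented in the eCRF. A boy who continues turoctocog alfa will often have a dose change within six months, and recording it as inhibitor treatment avoids withdrawal. Context also favours a narrower reading: the 5.3.4 sentence opens by making delay a matter of need and investigator decision, and the rationale concerns patients who do not benefit from treatment. Finally, later versions of 5.3.4 are seen only as amendment extracts with unchanged text left out, so the absence of an exemption is an inference.

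Most of this stands. It limits the reach and lowers the importance. It does not supply the missing condition, and a mandatory rule should not depend on how a site labels a dose change.

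A reader might also infer more than the documents support:

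- **That the primary result is affected.** A confirmed main-phase inhibitor is already in the numerator and denominator (18.2.2) and in the main-phase count of 50 (5.1).
- **That every boy with a transient inhibitor is withdrawn, or falls short of 100 ED.** A recorded dose adjustment avoids the rule, and on three-times-weekly or every-second-day dosing the shortfall is small or nil.
- **That no inhibitor test is assured before month 6.** That follows from Table 2-3 alone; 8.1.5.2 lists the test. The two places conflict and need aligning.
- **That clearance must be shown by two negative tests.** For treated patients 5.3.4 accepts a value below 0.6 BU/mL without asking for two. A stricter standard for untreated boys alone has no basis in the current text.

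**Conclusion.** The point holds as a minor, inexpensive improvement. As written, criterion 5 and the start rule require withdrawal of a boy whose confirmed inhibitor has cleared without recorded inhibitor treatment, contrary to the rationale for criteria 5 to 8.

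The certain loss for such a boy is his later extension-phase inhibitor testing. A shortfall against 100 ED is likely only on an unchanged once- or twice-weekly regimen after early confirmation, or on once-weekly dosing after confirmation at Visit 5. The loss is softened because data up to withdrawal are kept, an End of Trial visit with an inhibitor test follows within 28 days, and withdrawn patients may be replaced. The 100-ED goal is also an aggregate for at least 50 patients.

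The conclusion assumes that no unprinted part of 5.3.4 exempts cleared inhibitors. The number of boys is unknown and probably small.

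**What to change.** - **6.4, criterion 5, and the 5.3.4 start rule:** add the condition that the inhibitor is still at or above 0.6 BU/mL at the central laboratory. Use the below-0.6 BU/mL standard for clearance that 5.3.4 already applies to treated patients.
- **5.3.4, 8.1.6 and the Table 2-2 lead-in:** state that a patient who clears without inhibitor treatment continues preventive treatment on the extension schedule and still counts as a confirmed inhibitor case.
- **Table 2-3:** make the inhibitor test mandatory at inhibitor unscheduled visits, in line with 8.1.5.2, so that the titre needed for the decision is available.

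The cost is a short amendment, possibly an extra inhibitor sample per affected boy, and longer follow-up of a few boys. The primary analysis and sample size do not change.

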5.3.2 Treatment of Bleeds

~~During preventive treatment, break through bleeds may occur and require extra doses of turoctocog alfa.~~ Treatment of bleeds should be started as soon as a bleed is identified. All bleeds, mild/moderate and severe, can be treated at home. For severe bleeds (see Section 8.3.1.1) the Investigator should evaluate if the patient should be seen at the clinic. All bleeds must be reported to the clinic within 24 hours from onset of the bleed.

The dose for treatment of bleeds should aim at providing a post injection level of FVIII *according to Table 5-1 of at least 0.50 IU/mL or 50 IU/dL*.

...

Each administered dose (mL given, vial strength and time of day) as well as efficacy in treatment of bleeds will be registered in the diary and in the eCRF. *All treatments (excluding ITI treatment) administered in relation to bleeds must be recorded as 'treatment of bleeds', e.g. scheduled preventive treatment administered between start and stop time of a bleed must be registered as 'treatment of bleed'.*

...

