8.2 Assessments for Safety

8.2.2 FVIII antibodies

8.2.2.1 FVIII Inhibitors

Blood sampling for FVIII inhibitor test should be performed at a trough level, i.e. with a minimum of 48 hours turoctocog alfa treatment washout period. *The 48 hours washout period does not apply for patients on ITI treatment.*

...

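### Minor rule conflict: withdrawal criterion 9 and the prevention deadline in 5.3.1 make no exception for a boy whose inhibitor is found before any prevention, although 5.3.4 lets him start prevention after inhibitor treatment

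*Combined protocol and SAP*

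**What the plan says.** The withdrawal list in section 6.4 is mandatory: "A patient must be withdrawn if the following applies". The amendment that introduced twice-weekly dosing added criterion 9 to it (the section is printed there as 2.4): "Preventive treatment not initiated at the patient's age of 24 months". The stated reason is only to emphasise the existing deadline.

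That deadline is in 5.3.1: "the preventive treatment has to be commenced no later than when the patient reaches 24 months old", or after at most two bleeds needing turoctocog alfa, whichever is earlier. A boy already past 24 months at enrolment must start prevention at once.

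Section 5.3.4 offers continued treatment to boys who develop an inhibitor. On the start of inhibitor treatment it says "it has to start within 6 months from the time of diagnosis of inhibitor". Patients are evaluated at 12 months; a boy who is still positive may continue, up to 24 months in total, if the titre has fallen at least 20% from its peak. Once the inhibitor disappears, "the patient will continue in the extension phase at a time point decided by the Investigator, resuming/starting preventive treatment as recommended in this protocol". Criterion 8 withdraws a boy if "After completed inhibitor treatment (maximum 24 months), preventive treatment as described in the protocol is not resumed/started". Section 7 also allows inhibitor treatment for up to 24 months.

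**The concern.** Section 5.3.4 and criterion 8 both speak of starting, as well as resuming, prevention after inhibitor treatment. The natural case is a boy who had none before his inhibitor. Such a boy can exist, because section 18.2.2 lists bleed and surgery beside prevention as reasons for first FVIII treatment. If he turns 24 months while waiting for inhibitor treatment, receiving it, or waiting to start prevention afterwards, criterion 9 read literally withdraws him during a course that 5.3.4 permits. Section 8.1.5.2 lists the withdrawal criteria among the assessments at inhibitor visits, so site staff would meet criterion 9 at that point and could resolve it differently from site to site.

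He would lose trial-supplied inhibitor treatment, the central titres at inhibitor visits (at least every third month), reporting in the inhibitor cohort to the end of trial, and possible entry to the extension phase. Exclusion criterion 2 would bar him from re-entering.

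**Working it through.** The plan states no figure to reproduce, so this is a comparison of rules plus a timeline for one boy.

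**Inputs, in months**
- *a*: age at inhibitor diagnosis, below 24, with no prevention yet.
- *d*: delay before inhibitor treatment, 0 to 6 (5.3.4, criterion 5).
- *c*: length of inhibitor treatment, up to 24; going beyond 12 requires a titre decline of at least 20% (5.3.4, criteria 6 and 7).
- *g*: gap from the end of inhibitor treatment to the first preventive dose. The Investigator sets it and no limit is stated; 0 to 3 is my assumption.
- Limit: 24 (criterion 9, 5.3.1).

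**Condition.** If no preventive dose is given before inhibitor treatment ends, prevention starts at age *a + d + c + g*. The rules clash when *a + d + c + g* > 24, that is, when *a* > 24 − *d* − *c* − *g*. The 6-month course is illustrative.

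| Course *c* | *d*=0, *g*=0 | *d*=0, *g*=3 | *d*=6, *g*=0 | *d*=6, *g*=3 |
|---|---|---|---|---|
| 6 | *a* > 18 | *a* > 15 | *a* > 12 | *a* > 9 |
| 12 | *a* > 12 | *a* > 9 | *a* > 6 | *a* > 3 |
| 24 | any age | any age | any age | any age |

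**Latest start under 5.3.4, ignoring the gap.** *a* + 6 + 24 = *a* + 30: age 36 months for diagnosis at 6, 42 for 12, and 48 for 18.

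**Follow-up lost, illustrated by diagnosis at 18 months.** Inhibitor-visit time lost is *a + d + c* − 24.
- *c* = 12: 18 + 0 + 12 − 24 = 6 months, or 18 + 6 + 12 − 24 = 12 months. At one visit per 3 months, that is at least 2 to 4 visits.
- *c* = 24: 18 + 0 + 24 − 24 = 18 months, or 18 + 6 + 24 − 24 = 24 months. That is at least 6 to 8 visits.
- One End of Trial inhibitor test, due within 28 days, partly offsets each loss.

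**Effect of the gap alone.** Diagnosis at 14 months, no delay and a 9-month course give 14 + 0 + 9 = 23. Prevention 2 months later starts at 25, past the limit although treatment ended before it.

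**The two-bleed limb.** It can fall due at any age, so an inhibitor boy treated with turoctocog alfa for a second qualifying bleed would breach 5.3.1 even before 24 months. Only the age limb is repeated as a withdrawal criterion.

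**Boys enrolled after 24 months.** Entry is open below 6 years. For these boys prevention was not under way at 24 months, so criterion 9 taken literally catches them too, although 5.3.1 admits them and tells them to start at once.

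**The case against.** The best reply is that the documents should be read as a whole. The amended Summary has main-phase patients on prevention until 50 exposure days or until an inhibitor develops. The trial design caption places each patient in the main phase, the extension phase or the inhibitor cohort. The 24-month deadline and the wording on starting prevention after inhibitor treatment entered in the same amendment, so the authors presumably meant them to coexist. Criterion 9 already needs a sensible reading for boys enrolled late; the same approach would let 5.3.4 and criteria 5 to 8 govern inhibitor patients. This stands as evidence of intent. None of it is written as an override of a mandatory criterion.

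A second reply is that both rules can be met: criterion 9 asks only that prevention be initiated, and 5.3.4 does not forbid a preventive dose before inhibitor treatment, which is feasible with a low titre. This stands to the extent that the thresholds above are conditional on no such dose. A token dose given to a boy with an inhibitor merely to satisfy criterion 9 is not a sound solution.

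A third reply is that inhibitor treatment itself counts as prevention. The regimen table gives it a separate row, and 5.3.2 sets immune tolerance induction (ITI) apart when it recodes scheduled preventive doses given during a bleed: "All treatments (excluding ITI treatment) administered in relation to bleeds must be recorded as" treatment of bleeds. The line is less sharp where inhibitor treatment is only a small dose adjustment.

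The last amendment shown did write exemptions where it wanted them, for example "The 48 hours washout period does not apply for patients on ITI treatment", and no item in its list of changes names 6.4 or 5.3.1. That is weak evidence, because the final item covers unspecified minor inconsistencies and the consolidated final protocol is not supplied.

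**Conclusion.** The conflict holds as a minor one. It concerns only boys whose inhibitor is found before any prevention; a boy who began prevention first is not affected. Their number cannot be estimated from the documents and is probably small. Prevention is due after at most two treated bleeds, and the first scheduled post-dose inhibitor test is at 10 to 15 exposure days, so an unscheduled or surgery-related test would usually have to find the inhibitor. The thresholds describe one boy's timeline, not frequency, and rest on no preventive dose before inhibitor treatment ends and on the assumed gap.

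Several stronger inferences are not supported:
- *The primary result is biased.* Under the amended 18.2.2, a confirmed main-phase inhibitor counts in numerator and denominator whatever happens later.
- *The inhibitor is lost to safety follow-up.* Inhibitor formation is always an SAE and is followed to outcome under 12.2.2, although chronic conditions may be closed earlier.
- *The plan means to drop these boys.* The inhibitor cohort and criteria 5 to 8 point the other way.
- *Section 7 settles the matter.* Its exception was once tied expressly to the last-visit date and the current text is less clearly so limited; either way it governs how long inhibitor treatment may last, not when prevention must have begun. Nor does criterion 8 itself retain a boy: it only implies that prevention may first start after inhibitor treatment.

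**What to change.** Add the following to criterion 9 and to both limbs of the 5.3.1 deadline (24 months of age and two bleeds):

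> Not applicable from the first positive inhibitor test, if later confirmed, in a patient who has not started preventive treatment; for these patients section 5.3.4 and criteria 5-8 apply, including the start of prevention after inhibitor treatment.

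Counting from the first positive test covers a boy who turns 24 months before the confirmatory sample. Criteria 5 to 8 still limit how long he may stay.

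Also reword criterion 9 so that, for a boy enrolled after 24 months of age, it applies only if prevention is not started immediately as 5.3.1 requires.

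The cost is a few lines in two sections that the amendment adding criterion 9 already edited, with no extra visits, samples or data.
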